### **10.9 Efficacy**

#### **10.9.1 Primary Efficacy Analysis**

The SOC and treatment arms under WHO7 ordinal scale will be compared with respect to the primary endpoint using proportional odds models (ordinal logistic regression) adjusted for site and age. Treatment will be compared to SOC by testing whether the common odds ratio differs from 1.0 at day 15 using two-sided tests at 2.5% level of significance under the ITT population set, followed by PP population set. All modeling assumptions will be verified.

Separate 95% CI and p-values will be computed across each of the ordinal scale between SOC and treatment arms for both ITT and PP population sets. Multiple comparison techniques (to be detailed in the SAP) will be employed to ensure type I error is controlled to 5% for these comparisons.

If, following the Phase 2b interim analysis or final analysis, the primary endpoint changes for Phase 3, details will be written in the SAP, and a protocol amendment will be created.

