2.5 Sample Size

For the pilot phase, a sample of 150 patients (50 in Arm A, Arm B and SOC) will be recruited. To account for drop out of 10%, a total of 168 patients will be enrolled.

For the pivotal phase, A sample of 462 patients (231 in the SOC group and 231 in the active treatment group) achieves 90% power to detect a change in the log odds ratio of 0.5596 when the significance level (alpha) is 0.05 using a two-sided test. A log odds ratio of 0.5596 corresponds to an odds ratio of 1.75 comparing treatment to SOC. The sample size was estimated using the *Tests for Two Ordered Categorical Variables* module in PASS 14. To account for drop out of 10%, a total of 514 patients will be enrolled.

The sample size assumes that the distribution of patients on day 15 will be as shown in [Table 2](#), which is scenario 4 in the WHO master protocol (2020) for enrolled patients with moderate to severe disease under an odds ratio of 1.75.

Table 2 Distribution of Patients Across Outcome Categories at Day 15: SOC (WHO MP Scenario 4) and Treatment (Assuming OR of 1.75)

Outcome	Percent of Patients	
	SOC	Treatment
7. Death	2	1.0
6. Hospitalized & on mechanical ventilation or ECMO	1	0.6
5. Hospitalized & on non-invasive ventilation or high flow O2	2	1.2
4. Hospitalized & requires supplemental O2	5	3.03
3. Hospitalized not requiring supplemental O2	17	11.45
2. Not hospitalized but limitations on activities	36	31.90
1. Not hospitalized & no limitations on activities	37	50.70

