11.1 Primary Efficacy Analysis

For patients who died, their WHO7 responses of 7 (death) will be carried forward to all applicable visits. For example, a patient who died on Day 9, will be recorded as having WHO7 response of 7 on Day 11, 15 and 29.

The SOC and treatment arms under WHO7 ordinal scale will be compared with respect to the primary endpoint using proportional odds models (ordinal logistic regression) adjusted for site and age. Treatment will be compared to SOC by testing whether the common odds ratio differs from 1.0 at day 15 using two-sided tests at 2.5% level of significance under the ITT population set, followed by PP population set. All modeling assumptions will be verified.

The relevant SAS code for proportional odds model takes the following form, where Treatment represents SOC, Arm A, Arm B and Response represents the WHO7 ordinal scale categories.

```
proc logistic data=dataset;  
class Treatment Response Site/ param=ref ref=first;  
model Response = Treatment Age Site;  
run;
```

The odds ratio under the fitted proportional odds model will be reported for Arm A and B vs SOC, along with the Wald 95% CI and corresponding Chi-squared p-value. Score test p-value testing the assumption of proportional odds will also be reported. To adjust for multiple comparison, p-values must be < 0.025 to be considered statistically significant. P-values < 0.05 may still be considered as potentially promising for the next study phase.

In addition, counts and percentages of patients in each of the WHO-7 category will also be reported for each treatment arm.

Separate 95% CIs (Newcombe) and p-values (Chi-Squared test without continuity correction) will be computed across each of the ordinal scale between SOC and treatment arms A and B. To adjust for multiple comparison, p-values must be $< \frac{1}{280}$ or (0.05/14) to be considered statistically significant. The reason for adopting the most stringent rule for multiple adjustment is because this pilot phase of the study is essentially exploratory in nature, and care must be taken to minimize the event of a premature conclusion being made purely due to chance.

The above analyses will be done for ITT and PPS.

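### The supplementary Day 15 tests compare single WHO-7 categories, and an intermediate category has no guaranteed direction; cumulative cut-points would be readable from the same data (minor)

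*SAP*

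**What the plan says.** SAP 11.1 has two layers of Day 15 analysis on the WHO-7 scale.

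- **Primary.** A proportional odds model adjusted for site and age, "testing whether the common odds ratio differs from 1.0 at day 15 using two-sided tests at 2.5% level of significance", with each dose compared to SOC.
- **Supplementary.** Newcombe 95% intervals and uncorrected chi-squared p-values that "will be computed across each of the ordinal scale between SOC and treatment arms A and B". Each p-value must fall below 1/280, written as "0.05/14) to be considered statistically significant". Category counts and percentages are also tabulated, and a score test of proportional odds is reported.

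Protocol 10.9.1 has the parent sentence, "Separate 95% CI and p-values will be computed across each of the ordinal scale", and leaves the multiplicity method to the SAP. The synopsis repeats it.

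SAP 2.5 gives the planning assumptions: "a sample of 150 patients (50 in Arm A, Arm B and SOC) will be recruited", and Table 2 sets out the expected Day 15 distribution under SOC and under treatment. There, "A log odds ratio of 0.5596 corresponds to an odds ratio of 1.75 comparing treatment to SOC".

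SAP 2.1 says that Phase 2b will evaluate other constructions of the scale, including fewer categories. Protocol 10.3 lists the need for seven categories among the features to be reassessed for Phase 3. SAP section 11 specifies no analysis that collapses or cumulates categories.

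**The concern.** On an ordinal scale the readable binary questions are the cut-points: is the patient in category k or better? A single middle category gains patients from one side and loses them to the other, so its share can rise or fall under the same treatment effect. Category 2, "Not hospitalized but limitations on activities", is the clearest case. A significant fall there could mean that more patients reached category 1 or that fewer left hospital, and the test cannot say which.

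What is at stake is how the supplementary tests are read. The SAP attaches the label of statistical significance to each of them and says that it wants to avoid premature conclusions from the pilot. The pilot is also meant to inform the shape of the Phase 3 endpoint. For that purpose the Day 15 share discharged alive (categories 1–2) and the share in categories 1–3 are natural quantities, and neither is compared between arms as a Day 15 status.

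**Working it through.** **1. The plan's own figures.**

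- Threshold: 7 categories × 2 doses = 14, and 0.05/14 = 0.003571 = 1/280, as stated. Cut-points would give 6 × 2 = 12, so the divisor confirms single-category tests.
- Table 2 is the distribution behind the sample size. The proportional odds formula is n per arm = 6(z₀.₉₇₅ + z₀.₉₀)² / [(ln OR)²(1 − Σp̄³)], where p̄ is the mean of the two Table 2 columns. This gives 6 × (1.960 + 1.282)² / (0.5596² × 0.8736) = 230.4, so 231 per arm and 462 in total, as stated.

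**2. Direction of each category.** Start from the Table 2 SOC column (37/36/17/5/2/1/2% for categories 1 to 7) and multiply the odds of being in category k or better by OR. For category 2 at OR 1.75:

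- categories ≤1: odds 0.37/0.63 = 0.587; × 1.75 = 1.028; share 50.7%
- categories ≤2: odds 0.73/0.27 = 2.704; × 1.75 = 4.731; share 82.6%
- category 2 is the difference, 31.9%

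At OR 1/1.75 the two cumulative shares are 25.1% and 60.7%, and category 2 is 35.6%.

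| Category | SOC | OR 1.75 | OR 1/1.75 |
|---|---|---|---|
| 1 | 37.0 | 50.7 | 25.1 |
| 2 | 36.0 | 31.9 | 35.6 |
| 3 | 17.0 | 11.5 | 23.0 |
| 4 | 5.0 | 3.05 | 7.85 |
| 5 | 2.0 | 1.18 | 3.30 |
| 6 | 1.0 | 0.58 | 1.69 |
| 7 | 2.0 | 1.15 | 3.45 |

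The OR 1.75 column agrees with the printed treatment column of Table 2 to within 0.2 points; the printed column sums to 99.88%. Only category 2 falls in both directions. Categories 3 to 6 fall with benefit and rise with harm.

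**3. Dependence on the control mix.** Take an assumed sicker SOC distribution, 10/15/20/25/15/5/10%, which is not in the documents. OR 1.75 now raises category 2 from 15.0% to 20.6% and category 3 from 20.0% to 22.0%. The consistent sign of category 3 in Table 2 is therefore a property of that control column.

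**4. The cumulative shares.**

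| Cut-point | SOC | OR 1.75 | OR 1/1.75 |
|---|---|---|---|
| ≤1 | 37.0 | 50.7 | 25.1 |
| ≤2 | 73.0 | 82.6 | 60.7 |
| ≤3 | 90.0 | 94.0 | 83.7 |
| ≤4 | 95.0 | 97.1 | 91.6 |
| ≤5 | 97.0 | 98.3 | 94.9 |
| ≤6 | 98.0 | 98.8 | 96.6 |

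All six rise with benefit and fall with harm. Under proportional odds this is true for any control mix.

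**5. Power.** Exact binomial enumeration of the uncorrected chi-squared test with 50 against 50: all outcome pairs are listed and the probabilities of those with p below the threshold are summed. Cut-points use 0.05/12 = 0.00417 and single categories 0.05/14. OR 2.5 and 1/2.5 are assumptions.

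| Effect | ≤2 | Category 2 | ≤3 | Category 3 |
|---|---|---|---|---|
| OR 1.75 (planned) | 4.0% | 0.7% | 1.0% | 1.3% |
| OR 2.5 | 12.9% | 2.2% | 2.1% | 3.5% |
| OR 1/2.5 (harm) | 24.1% | 0.55% | 9.8% | 3.35% |

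For scale, the common odds ratio test at 50 per arm, 0.025 and OR 1.75 has power Φ(0.5596 × √(50 × 0.8736/6) − 2.241) = Φ(−0.73), about 23%.

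**The case against.** The strongest reply is that little depends on these tests. The primary model is cumulative, has one direction, uses all six cut-points, and keeps its own 0.025 threshold, so the 14 supplementary tests take no alpha from it. The SAP calls the pilot phase exploratory and ties no decision rule to them. Category counts are tabulated, so a reader can add up any cut-point. All of this stands, and it is why the point is minor.

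Four stronger readings are tempting, and the documents do not support them.

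- *That the sign means nothing for categories 2 to 6.* Under Table 2 this is true of category 2 only. Categories 3 to 6 have a consistent sign there, and a reversal for category 3 needs a control mix that the documents do not give. Categories 1 and 7 are already cut-points.
- *That the plan never examines discharge or oxygen.* SAP 11.8.2 analyses time to discharge with death as a competing risk, SAP 11.7.2 time to SpO₂ above 94% on room air, and SAP 11.9 Day 15 and Day 28 mortality. What is missing is a Day 15 status comparison. Time to discharge is a different quantity, because a patient who is discharged and then readmitted or dead by Day 15 still counts as an event.
- *That cut-points are more powerful throughout.* Under benefit, ≤3 has slightly less power than category 3 alone. By simulation, the chance of at least one significant supplementary result per dose rises only from about 7% to 10% at OR 1.75, and from 27% to 32% at an assumed OR of 2.5.
- *That a significant category 2 result under benefit is always a fall.* It usually is, but at OR 1.75 about 0.04% of trials would show a significant rise, out of 0.7% that are significant at all.

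**Conclusion.** The point holds as a minor one about interpretation. The supplementary tests use single categories, and on the plan's own Table 2 a lower category 2 share is compatible with benefit (31.9%) and with equal harm (35.6%). Each cut-point has one reading.

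The primary analysis, its error control and the sample size are unaffected. At the planned effect no supplementary test in either form has power much above 6% (category 1 alone: 6.0% at 0.05/14, 6.3% at 0.05/12). The results therefore serve best as estimates with intervals. The clearest power gain is at ≤2, and it is larger for detecting harm. The cost is a small loss at ≤3 under benefit.

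The figures assume proportional odds, the Table 2 SOC column and 50 evaluable patients per arm. The reversal for category 3 rests on an assumed sicker mix. Cut-point odds ratios would add something that the planned score test does not: that test is global, and its p-value does not show at which split a treatment effect departs from a common odds ratio.

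**What to change.** In SAP 11.1, replace the seven single-category tests per dose with the six cumulative contrasts, WHO-7 ≤1 to ≤6. Keep the Newcombe intervals and the same chi-squared test, and report the odds ratio at each cut-point beside the difference. The family becomes 12 tests and the threshold 0.05/12 = 0.0042. Keep counts and percentages by category as description.

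Label ≤2 as discharged alive, and ≤3 as *discharged, or in hospital without supplemental oxygen*. The shorter label *alive off oxygen* is not safe for ≤3, because categories 1 and 2 do not record oxygen use at home. Note that ≤6 largely repeats the Day 15 mortality comparison in SAP 11.9.

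The cost is SAP and table-shell wording, and a matching change to the sentence in protocol 10.9.1 and the synopsis at the next amendment. No new data are needed, and the output would bear directly on whether Phase 3 needs all seven categories.

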11.2 Secondary Efficacy Analysis: General Population Considerations

All secondary efficacy analyses will be performed for ITT and PPS.

11.3 Secondary Efficacy Analysis: Time to Event General Considerations

Time to event endpoints will not be evaluated if any subjects experienced an event prior to randomization in any of the treatment arms.

Time-to-event endpoints without competing risk will be analysed for each dosing group using the Kaplan-Meier (KM) method. Medians (with corresponding 95% confidence intervals) and quartiles (25th and 75th percentiles), minimum, and maximum survival times will be presented. In addition, the number of patients with an event and the number of censored patients will also be reported. The corresponding Kaplan-Meier survival plot will also be presented along with number at risk statistics at the appropriate time points. Adjusted hazard ratio, 95% CIs and p-values between active treatment groups to SOC under Cox proportional hazard model with age, site and treatment groups as covariates will be reported.

Time-to-event endpoints with competing risk will be analysed for each dosing group using the Cumulative Incidence Function-CIF (KM) graphical display. Adjusted hazard ratio, 95% CIs and p-values between active treatment groups to SOC under Fine-Gray sub-distribution hazard model with age, site and treatment groups as covariates will be reported. Competing risk is identified by the presence of death outcome, which prevent the observation of the current outcome of interest.

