### 5.1 Inclusion Criteria

1. Male and female subjects aged  $\geq 18$  years of age
2. Confirmed coronavirus infection
  - a) Positive real-time fluorescence polymerase chain reaction of the patient's respiratory or blood specimens for SARS-CoV-2 nucleic acid
  - b) Viral gene sequences in respiratory or blood specimens that are highly homologous to SARS-CoV-2
  - c) Any other diagnostic test accepted by local regulatory authorities
3. Must be hospitalized and requiring supplemental oxygen, or on non-invasive ventilation or high flow oxygen devices (Score of 4 or 5 on WHO Ordinal Clinical Scale)
4. Female subjects of childbearing potential who are sexually active with a non-sterilized male partner must use at least 1 highly effective method of contraception (e.g. oral contraceptives, intrauterine device, diaphragm plus spermicide) from the time of screening and must agree to continue using such precautions for 90 days after the final dose of study drug(s)

5. Non-sterilized males who are sexually active with a female partner of childbearing potential must use condom plus spermicide from day 1 through 90 days after receipt of the last dose of study drug(s)
6. Subjects (or legal designate) must have the capacity to understand, sign and date a written, informed consent form and any required authorization prior to initiation of any study procedures

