## **5.2 Exclusion Criteria**

1. Patients with vasodilatory shock, orthostatic hypotension, hypotension, or tachycardia at screening/baseline
2. Patients experiencing cerebral hemorrhage or cerebral infarction at baseline
3. ALT/AST > 5 times the upper limit of normal; Child-Pugh Score 10 to 15.
4. Stage 4 severe chronic kidney disease or requiring dialysis (i.e. eGFR < 30)
5. Patients on mechanical ventilation or extracorporeal membrane oxygenation (ECMO)
6. Patients taking droxidopa
7. Pregnant and lactating women and those planning to get pregnant
8. Known or suspected allergy to the trial drug or the relevant drugs given in the trial
9. Presence of other disease that may interfere with testing procedures or in the judgement of the Investigator may interfere with trial participation or may put the patient at risk when participating in this trial
10. Know inability of patient to comply with the protocol for the duration of the study
11. Involvement in a clinical research study within 4 weeks prior to screening and/or prior enrollment in the study or plan to participate in another interventional clinical trial during the study period. Participation in observational registry studies is permitted.

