## 7.3 Visits

### 7.3.1 Visit 1 (Screening/Baseline/Enrollment)

At Visit 1, information will be collected for evaluation of trial eligibility by provided information as follows and patients will be randomized and dosed after confirmation of eligibility:

- Signing ICF (prior to any trial-related activities)
- Inclusion criteria and exclusion criteria
- Demographics (gender, date of birth, race and ethnic origin) and relevant medical and surgical history
- Confirmation of COVID-19 diagnosis (SARS-CoV-2 RNA confirmation). Include dates of onset of symptoms (if available) and initiation of treatment.
- Pregnancy test (females of reproductive age; Romania: Serum beta-human chorionic gonadotropin [ $\beta$ -HCG]; Rest of World: Serum beta-human chorionic gonadotropin [ $\beta$ -HCG] or urine test is acceptable)
- Vital signs measurements (including pulse, respiration rate, body temperature, systolic and diastolic blood pressure measured with the patient in a seated position [if possible] after  $\geq 3$  minutes of rest), and SpO2. Body weight and height will be included for the screening visit only
- Limited Physical Exam
- Assess baseline measures of clinical support
  - Hospitalized
  - Oxygen requirement
  - Non-invasive mechanical ventilation (via mask)
  - Mechanical ventilator requirement (via endotracheal tube or tracheostomy tube)
  - ECMO requirement
  - Ordinal Scale Assessment
    1. Not hospitalized, no limitations on activities
    2. Not hospitalized, limitation on activities
    3. Hospitalized, not requiring supplemental oxygen
    4. Hospitalized, requiring supplemental oxygen
    5. Hospitalized, on non-invasive ventilation or high flow oxygen devices
    6. Hospitalized, on invasive mechanical ventilation or ECMO
    7. Death
  - For the purposes of eligibility/baseline the worse score from the previous day (Day -1) will be used
  - NEW Score
- Safety laboratory testing
- Child-Pugh Score
- Cytokine Markers
- PaO2 and PaO2/FiO2 ratio
- ECG
- VAS (if possible)
- Extent of Dyspnea (if possible). For the first questionnaire (at baseline), the patient compares their current shortness of breath to their shortness of breath when they are well.)
- Concomitant medications documented
- Randomization\* after eligibility confirmation. All screening/baseline procedures must be completed prior to randomization and administration of study medication.

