11.6 Secondary Efficacy Analysis: Respiratory Support

For the part of the analysis, respiratory support is defined as:

- Any respiratory support (any of Oxygenation only, Mechanical Ventilation (Invasive and non invasive), ECMO)
- Oxygenation only
- Invasive Mechanical Ventilation
- Non Invasive Mechanical Ventilation
- ECMO

11.6.1 Rate of Respiratory Support: Oxygenation only, Mechanical Ventilation (Invasive and non invasive), ECMO

Counts and percentages of patients for respiratory support at least once will be reported for each treatment arm. If patients were eligible for respiratory support but did not receive one due to lack of resources, an additional analysis on counts and percentages of patients required to receive respiratory support will be reported for each treatment arm. Separate 95% CIs (Newcombe) and p-values (Chi-Squared test without continuity correction) will be computed between SOC and treatment arms A and B for patients with at least one respiratory support.

11.6.2 Duration of Respiratory Support: Oxygenation only, Mechanical Ventilation (Invasive and non invasive), ECMO

Counts and percentages of patients with the following categories (based on total number of hours of respiratory support) will be reported for each type of respiratory support and for each treatment arm. The duration calculation is only applicable to patient with respiratory support. For patients with ongoing respiratory support with no end date and time at data cut off, the date of data cut off will be used to calculate the end date for the ongoing at time of data cut off category.

The duration is defined as:

Date and time at end of respiratory support-Date and time at end of respiratory support.

- < 6 hours
- \geq 6 hours but < 12 hours
- \geq 12 hours but < 24 hours
- \geq 24 hours but < 72 hours
- \geq 72 hours but < 120 hours
- > 120 hours
- Ongoing at time of data cut off (\geq 6 hours) [The hour can be amended based on real data]
- Ongoing at time of data cut off (\geq 12 hours) [The hour can be amended based on real data]
- Ongoing at time of data cut off (\geq XX hours) etc...
- Prolonged respiratory support (consecutive respiratory support for 21 days with at least \geq 6 hours per day)

Separate 95% CIs (Newcombe) and p-values (Chi-Squared test without continuity correction) will be computed between SOC and treatment arms A and B for prolonged respiratory support.

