11.6.3 Time to Respiratory Support: Oxygenation only, Mechanical Ventilation (Invasive and non invasive), ECMO

The time to respiratory support (Day) is defined as:

Date of first respiratory support – Date of Baseline Assessment + 1.

If the patient did not require respiratory support, the patient will be censored at the last known date the patient is known to not require respiratory support:

Final Date of Confirmation of no respiratory support needed - Date of Baseline Assessment + 1.

If a patient died before obtaining respirator support, the patient will be censored as a competing risk based on the following:

Date of Death - Date of Baseline Assessment + 1.

11.6.4 Time from first Oxygenation Support to first termination of Oxygenation Support:

This calculation is only applicable for those with oxygenation support.

The time to from first oxygenation support to first termination of oxygenation support is defined as:

Date of first termination of oxygenation support – Date of first oxygenation support + 1.

If the patient was still on oxygenation support, the patient will be censored at the last known date the patient is known to still on oxygenation support:

Final date of confirmation of still on oxygenation support - Date of first oxygenation support + 1.

If a patient died before terminating oxygenation support, the patient will be censored as a competing risk based on the following:

Date of Death - Date of Baseline Assessment + 1.

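### Under SAP 11.3 one patient already on non-invasive ventilation at entry removes time to that event for all arms, and the ventilation rates in 11.6.1 and interim item 5 are not limited to new use

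*SAP*

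**What the plan says.** SAP 11.3 sets one condition for every time-to-event analysis: "Time to event endpoints will not be evaluated if any subjects experienced an event prior to randomization in any of the treatment arms". It gives no threshold, no risk set and no fallback.

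Protocol 5.1, inclusion 3, describes who enters: "Must be hospitalized and requiring supplemental oxygen, or on non-invasive ventilation or high flow oxygen devices". Exclusion 5 in Protocol 5.2 bars mechanical ventilation and ECMO. To agree with inclusion 3, that must mean invasive ventilation.

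SAP 11.6 lists five support categories: any support, oxygenation only, invasive ventilation, non-invasive ventilation and ECMO. The analyses that matter here are:

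- **11.6.1 (rate):** "Counts and percentages of patients for respiratory support at least once will be reported for each treatment arm". Newcombe intervals and chi-squared p-values are "computed between SOC and treatment arms A and B for patients with at least one respiratory support".
- **11.6.3 (time to support):** "Date of first respiratory support – Date of Baseline Assessment + 1".
- **11.6.4 (time on oxygen):** the clock starts at first oxygen support and stops at its first termination.
- **SAP 14.1, interim item 5:** invasive and non-invasive ventilation are pooled and counted if received by Day 15.

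None of these requires support to have started after randomization. The secondary objective in SAP 2.2.2 and Protocol 3.1 is the incidence and duration of new mechanical ventilation, and Protocol 10.9.2 speaks of its initiation.

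**The concern.** The 11.3 rule is all-or-none, while eligibility allows the very state that triggers it. A patient who meets every entry criterion can delete time to NIV for the whole trial. Nothing in 11.6.3 prevents this: support that began the day before baseline gets a time of -1 + 1 = 0, and earlier starts get negative times.

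The rate has a related gap. If ventilation in use at entry counts as an event, the table mixes the patients' starting state with what happened after randomization.

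What is at stake is secondary but not empty. The rate of mechanical ventilation is a listed secondary endpoint (SAP 2.3.2), the SAP's mechanical ventilation includes non-invasive, and SAP 2.1 says that Phase 2b data will be used to select and rank the secondary endpoints.

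**Working it through.** **Inputs from the documents.** Phase 2b: 50 per arm, 10% dropout, 168 enrolled, 1:1:1 (SAP 2.1 and 2.5). Secondary tests: two-sided 5% (Protocol 10.9.2). The plan's enrolment figure reproduces: 50/0.9 = 55.6, rounded up to 56, and 3 × 56 = 168.

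**Assumed inputs.** The share q on NIV at entry and the rates r of new NIV are in neither document. Score 5 also covers high flow oxygen, so even the score-5 share would not give q.

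**Step 1: chance that 11.3 removes time to NIV.** This is P(at least one patient on NIV at entry) = 1 - (1 - q)^168.

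| q | Chance removed |
|---|---|
| 0.5% | 57% |
| 1% | 82% |
| 2% | 97% |
| 5% | >99.9% |

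The chance reaches 50% at q = 1 - 0.5^(1/168) = 0.41%. With 150 patients the four figures are 53%, 78%, 95% and >99.9%.

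**Step 2: any support.** Every eligible patient is on oxygen, NIV or high flow oxygen at entry. Time to any support is therefore always removed, and its literal rate is 56/56 in each arm. The Wilson lower limit is 56/(56 + 1.96²) = 0.936, so the Newcombe interval for the difference is 0 ± 6.4 points whatever the drug does.

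**Step 3: three ways to count NIV.** By randomization the expected q is the same in each arm.

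- As written, read literally: rate q + (1 - q)r, n = 56.
- New use over all randomized patients: rate (1 - q)r, n = 56, with patients on NIV at entry as non-events.
- New use in patients at risk: rate r, n = 56(1 - q).

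The first two have the same expected difference, (1 - q)(r1 - r2). The third has r1 - r2 because its denominator is smaller.

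**Step 4: precision at q = 20%.** SD = sqrt(A(1-A)/n + B(1-B)/n) for rates A and B. Power is the two-sided 5% normal approximation.

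| New use, SOC vs active | Counting | Rates (%) | Difference | SD | Power |
|---|---|---|---|---|---|
| 30 vs 15 | as written | 44 vs 32 | 12 | 9.10 | 26% |
| 30 vs 15 | new, all randomized | 24 vs 12 | 12 | 7.17 | 39% |
| 30 vs 15 | new, at risk (n = 44.8) | 30 vs 15 | 15 | 8.68 | 41% |
| 10 vs 5 | as written | 28 vs 24 | 4 | 8.28 | 8% |
| 10 vs 5 | new, all randomized | 8 vs 4 | 4 | 4.47 | 15% |
| 10 vs 5 | new, at risk (n = 44.8) | 10 vs 5 | 5 | 5.54 | 15% |

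The difference is the same in the first two rows of each block, so the cost in patients is the ratio of variances. For 30 vs 15 it is (0.2464 + 0.2176)/(0.1824 + 0.1056) = 1.61. For 10 vs 5 it is (0.2016 + 0.1824)/(0.0736 + 0.0384) = 3.43. A risk ratio formed from the literal rates would be 32/44 = 0.73 or 24/28 = 0.86, against 0.50 for new use.

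**Step 5: 11.6.4.** Patients enter already on support, so its clock can start before randomization. A first termination can also fall before randomization, for example in a patient stepped up from plain oxygen to NIV. The section is then exposed to the same 11.3 rule.

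**The case against.** The strongest reply is that a reader might infer a biased treatment effect, and the documents do not support that. The Newcombe reference in SAP 17 concerns a difference between proportions, and 11.6.1 plans no ratio. Steps 3 and 4 show that the literal count leaves that difference unbiased for new use over all randomized patients. The smaller difference relative to the at-risk group comes from the denominator. This stands, and it reduces the harm in the rate to inflated displayed rates and lost precision. At 10% vs 5% the test is weak under any of the three counts.

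It can also be said that new use was meant throughout, since the objective says so, and that the mock shells cited in SAP 16 may define it. They may settle the rate, and they are not in the documents. They are not a reason to leave 11.3 as it stands: that rule expressly anticipates events before randomization and answers them by deleting the analysis.

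Further limits also stand. Time to NIV is not a listed endpoint, although Protocol 10.9.2 names initiation of mechanical ventilation as a time-to-event analysis. SAP 11.6 already separates invasive from non-invasive ventilation, and only interim item 5 pools them. Item 5 is descriptive. Exclusion 5 largely protects invasive ventilation and ECMO, though earlier use that has ended could still trigger 11.3.

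**Conclusion.** The concern holds as a secondary-endpoint defect that should be corrected. Followed exactly, 11.3 removes time to any support with certainty. It removes time to NIV as soon as one patient enters on NIV, which is more likely than not once the entry share passes 0.41% of 168. That loss is likely and not certain, because the share is unknown.

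The rate definitions in 11.6.1 and interim item 5 do not, on their text, carry out the stated objective of new use. The cost is precision and readability: 26% power against 39% or 41% in the larger-effect example, and 8% against about 15% in the smaller one, all under assumed rates.

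Two stronger readings go too far. The plural wording of 11.3 might suggest that one early event cancels every time-to-event analysis, including mortality. Reading it endpoint by endpoint is narrower and more natural, and it is the reading used here. Nor does any of this reach the primary endpoint, which is Day 15 ordinal status. The SAP itself calls this stage essentially exploratory (11.1).

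**What to change.** - **11.3:** replace the rule with a risk set for each endpoint. Patients who already meet the event at randomization leave that endpoint only, and their number is reported by arm.
- **11.6.1 and interim item 5:** count as events only support of the given type newly started after randomization. Keep all randomized patients in the denominator, which preserves the ITT set required by 11.2, and give the at-risk subset as a supporting analysis. State that patients on that type at randomization are non-events.
- **11.6.3:** time the first new start after randomization in patients not on that type at randomization.
- **Interim item 5:** show invasive and non-invasive ventilation separately.
- **Any support:** drop it as an incidence and time-to-first-support comparison.
- **11.6.4:** start the clock at randomization.
- **Definition:** fix status at randomization explicitly. Protocol 7.3.1 takes the worse ordinal score from the previous day as baseline, while SAP 3.2 takes the Day 1 value.

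The cost is SAP wording and code. Support type is already recorded at Visit 1 and daily in hospital, so no new data are needed. The downside is that risk sets will differ between time-to-event endpoints, and time to NIV will describe a subgroup defined at baseline.
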